Aim 2 Sample size. We will recruit 32 subjects to be randomized to an intervention and control arm with a ratio of 1:1 ($n = 16$ per study group), using a random number generator. A sample size comparable to a prior study of cellular phone and internet-based intervention on BP reduction that showed medium to high effect sizes (ES $f = 0.395$) on BP reduction.⁴⁹ Using an estimated ES of $f = 0.39$ for the within-subject effect (Time), we conducted a power analysis for a mixed design ANCOVA with 2 groups, 2 measurements per subject, and $r = .5$ for the bivariate correlation between two measures tested at $\alpha = 0.05$. To achieve 70% power for the significance test of the within-between interaction effect, a sample of $N = 28$ will be needed. Anticipating a 7-11% attrition rate⁴⁹ based on the previous study,⁴⁹ an initial $N = 32$ will be needed to achieve 70% power to test preliminary impact. The low power is a limitation; we will attempt to recruit more within the timeframe to reach a higher power level.

Aims 1 and 2 Site for subject enrollment. UNLV is the largest university in Nevada with over 30,000 undergraduate and graduate students, and it is most diverse university in the nation. This increases the potential for inclusive recruitment of different race/ethnicities that reflect the changing demographics of the state and nation.

Aim 2 Enrollment and recruitment. We will use recruitment strategies that have been successful in the PI's previous studies, including posting research flyers around campus, UNLV Rebel Announcements, UNLV Today (monthly), Student E-Newsletters from Department (SEND), and UNLV Graduate & Professional Student Association. Recruitment will occur face-to-face with students at sites around campus (once campus is opened). Subjects will be screened privately for inclusion (1. During the initial zoom meeting going over the informed consent in addition to 2. Having high blood pressure, meet via face-to-face following CDC guidelines for 5-10 minutes).

Aim 2 and Exploratory Aim Study Procedures - MOBILE Intervention

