Baseline data collection. Baseline data collection (using Qualitrics) will occur before the start of the educational session, described below. Subjects with blood pressure value less than 120/80 mm Hg during this visit (second blood pressure reading) will no longer qualify for this study. The gold standard BP measurement using a sphygmomanometer through auscultation will be taken twice, five minutes apart to be averaged. Other baseline data include: anthropometry (height and weight), Automated Self-Administered 24-Hour Dietary Assessment Tool (ASA24) focusing on sodium intake, pre-test Hypertension Knowledge-Level Scale (HK-LS), and initial motivational level assess (using Qualitrics) using the study's iPads. We have two research iPads that are only designated for this project. The subjects will not use their own devices and the link are not send to subjects. It is already set up to collect data from the subjects. We locked the screen on the iPads so only the questionnaires can be accessed.

Aim 2 Educational session, all subjects. The PI or RA will provide a brief one-on-one or group educational talk (no more than 2 subjects, to separate intervention and control group subjects) before the 4-week trial on the importance of SMBP, elevated BP regarding CVD risk, the role of motivation in adopting lifestyle behavior, and specific behaviors to reduce BP. This is akin to HTN risk reduction advice received in an office visit.

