MOBILE Intervention in College Students with Elevated Blood Pressure

Version Date: 05/19/2021

Statistical Analysis Plan

Statistical Design and Power

Sample size. We will recruit 32 subjects to be randomized to an intervention and control arm with a ratio of 1:1 ($n = 16$ per study group), using a random number generator. A sample size comparable to a prior study of cellular phone and internet-based intervention on BP reduction that showed medium to high effect sizes (ES $f = 0.395$) on BP reduction.⁴⁹ Using an estimated ES of $f = 0.39$ for the within-subject effect (Time), we conducted a power analysis for a mixed design ANCOVA with 2 groups, 2 measurements per subject, and $r = .5$ for the bivariate correlation between two measures tested at $\alpha = 0.05$. To achieve 70% power for the significance test of the within-between interaction effect, a sample of $N = 28$ will be needed. Anticipating a 7-11% attrition rate⁴⁹ based on the previous study,⁴⁹ an initial $N = 32$ will be needed to achieve 70% power to test preliminary impact. We acknowledge that the low power level is a limitation in our pilot study; therefore, we will attempt to recruit more within the timeframe to reach a higher power level.

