Data Analysis. Aim 2: We will perform preliminary descriptive analyses on all variables, use Pearson's correlation (r) to assess relationships between primary and secondary outcome variables at each data collection point, and calculate Pearson's r to assess the stability of each outcome variable pre- and post-intervention. To evaluate feasibility and acceptability, we will use content analytic methods to identify students' likes and dislikes and suggestions for future app improvement.⁶⁵ Thematic analysis of interviews will be conducted to describe the elements of feasibility and acceptability as perceived by subjects. Participation rate will be calculated as the percentage of students enrolled out of all eligible students who are invited to participate in the study; engagement will be calculated as a percentage of students' available data out of all the intended data points. **Exploratory Aim.** "The intervention group will have a significantly greater reduction in BP and sodium intake and greater increase in HTN knowledge from baseline to completion, compared to control group." A 2x2x2 mixed design ANCOVA will be performed for each of the above primary and secondary outcomes, with Study Group (Intervention vs. Control) as the between-subject factors, years of age as the covariate. A Time effect on an outcome variable would indicate the impact of the **MOBILE** intervention on the outcome measure in college students with elevated BP.

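### Is the participation rate uncomputable because the SAP does not say who counts as invited or enrolled?

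*SAP*

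**What the plan says.** The SAP, Data Analysis, Aim 2, defines the measure in one clause: "Participation rate will be calculated as the percentage of students enrolled out of all eligible students who are invited to participate in the study". It gives no expected value, target or threshold, and does not say when a student becomes invited or enrolled.

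The Protocol gives the setting. Under Aims 1 and 2 Site for subject enrollment: "UNLV is the largest university in Nevada with over 30,000 undergraduate and graduate students". Under Aim 2 Enrollment and recruitment, the strategies include "posting research flyers around campus, UNLV Rebel Announcements, UNLV Today (monthly), Student E-Newsletters from Department (SEND" and in-person recruitment on campus. Screening is private and has two parts: the Zoom meeting at which consent is discussed, and an in-person step described as "Having high blood pressure, meet via face-to-face following CDC guidelines for 5-10 minutes". Baseline data collection adds a second check: "Subjects with blood pressure value less than 120/80 mm Hg during this visit (second blood pressure reading) will no longer qualify for this study".

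The SAP, Sample size, plans to randomise 32 students and adds that "we will attempt to recruit more within the timeframe to reach a higher power level".

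**The concern.** Advertising comes before anyone's BP is known. If a student who sees a flyer or receives a newsletter has been invited, the denominator is the number of eligible students among all those reached. That number cannot be obtained, because the BP of students who never attend is unknown. If the invitation comes only after eligibility is established, the denominator can be counted, but it leaves out everyone lost before BP is measured. The two versions could give very different percentages, and the SAP does not say which it means.

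*Enrolled* is open too: it could mean consented, still qualifying at baseline, or randomised. At stake is one of the two calculated percentages in the feasibility and acceptability assessment. A reader could take a high value as evidence of easy recruitment when it shows only that few students dropped out after being found eligible.

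**Working it through.** The plan states no participation rate, so there is no figure to reproduce. The check compares the readings and then sizes what stays open. Only 32 (SAP, Sample size) and 30,000 (Protocol, Site for subject enrollment) come from the documents; every other count is assumed.

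**Which reading does the text support?**

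- The denominator is restricted to eligible students. Under the Protocol, eligibility is learned at screening and re-checked at baseline, so only screened students can be classified.
- The Protocol presents flyers, announcements and newsletters as recruitment strategies and does not call them invitations. Its one use of the verb *invite* is for asking an individual silent subject to a meeting.
- The broad reading cannot be computed from data the study will hold. An analyst therefore could not adopt it, even by mistake.

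**Broad reading, for illustration.** Rate = 32 / (students reached × share eligible).

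| Reached (assumed) | Share eligible (assumed) | Denominator | Rate |
|---|---|---|---|
| 500 | 10% | 50 | 64.0% |
| 3,000 | 10% | 300 | 10.7% |
| 30,000 | 40% | 12,000 | 0.27% |

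**Narrow reading.** Rate = 32 / students found eligible, with exact 95% intervals.

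| Found eligible (assumed) | Rate | 95% interval |
|---|---|---|
| 32 | 100% | 89.1% to 100% |
| 36 | 88.9% | 73.9% to 96.9% |
| 40 | 80.0% | 64.4% to 90.9% |
| 64 | 50.0% | 37.2% to 62.8% |

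**Size of the gap between readings.** Taking 300 to 12,000 for the broad denominator and 32 to 40 for the narrow one, the ratio runs from 80.0/10.67 = 7.5 to 100/0.2667 = 375. With 500 reached and 10% eligible it is 80.0/64.0 = 1.25. With 64 found eligible, the narrow rate of 50.0% falls below that broad rate of 64.0%. The gap is therefore a product of the assumed ranges and says nothing firm about this trial.

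**What stays open within the narrow reading.** Suppose 40 students qualify at screening, 4 fall below the BP limit at baseline, 4 decline and 32 are randomised. Counting eligibility at screening gives 32/40 = 80.0%. Counting it at baseline gives 32/36 = 88.9%. The difference is 8.9 percentage points, while the exact interval around 80.0% is 90.9 − 64.4 = 26.5 points wide.

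**What the narrow rate does not show.** Suppose 80 are BP-screened, 40 are eligible and 32 are randomised. The rate is 80.0% whether 100 or 400 students made contact, while overall yield is 32/100 = 32% or 32/400 = 8%.

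**The case for a change.** The strongest case for a change has three parts.

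First, the definitions really are missing, and a careless pairing gives nonsense. If 36 students consent, 32 still qualify at baseline, and consented is set against still qualifying, the rate is 36/32 = 112.5%. The omission stands. But a participation rate above 100% exposes itself, and an analyst would draw numerator and denominator from the same sequence of steps.

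Second, screening overlaps with the consent discussion, so many students in the narrow denominator may already be inclined to join. A high percentage would then say little about interest on campus. This also stands as a limit on interpretation. It is not a fault in the measure: the SAP calls it a participation rate among eligible students, not uptake among all students contacted.

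Third, the team hopes to recruit beyond 32, which depends on how many contacts each randomised student costs, and contacts not logged at the time are lost. A log would be useful. However, the sentence about recruiting more concerns power, and nothing in it relies on the participation rate. The documents describe no log, but they do not rule one out. Nor do they show that the reach of newsletters is unmeasurable; what is unknowable is the BP of people who never attend.

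**Conclusion.** The concern does not call for a change. The SAP leaves *invited* and *enrolled* undefined, but only one reading of the denominator fits both its restriction to eligible students and the order of recruitment and screening: students found eligible and then offered participation. Analysts would adopt that reading, and it gives a sound descriptive percentage.

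The remaining looseness is which BP check settles eligibility. In the assumed example it moves the rate between 80.0% and 88.9%, well inside the sampling uncertainty at this sample size. No target, stopping decision or test depends on the rate, and the comparison between groups is untouched.

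This conclusion assumes that the study counts the students it screens and finds eligible, as any trial must in order to apply its own entry criterion. Ordinary participant-flow counts in the final report, with baseline exclusions shown apart from refusals, would make the percentage clear without amending the plan.

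### The Exploratory Aim is framed as a significance test read from a Time effect, in a pilot with stated power of 70%; the between-arm difference in change with its 95% CI should be the result

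*SAP*

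**What the plan says.** The SAP's Exploratory Aim is a directional hypothesis against control: "The intervention group will have a significantly greater reduction in BP and sodium intake", together with a larger gain in hypertension knowledge. The analysis is stated as "A 2x2x2 mixed design ANCOVA will be performed for each of the above primary and secondary outcomes", with study group as the between-subject factor and age as the covariate. The plan then says how the output will be read: "A Time effect on an outcome variable would indicate the impact of the" MOBILE intervention.

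The sample-size section, which is nearly the same in the protocol (Aim 2 Sample size) and the SAP, sizes the study for a test of the Group x Time interaction: "To achieve 70% power for the significance test of the within-between interaction effect, a sample of $N = 28$ will be needed". Enrolment is set at 32, 16 per arm, to allow for 7-11% attrition. The SAP is open about the consequence ("We acknowledge that the low power level is a limitation in our pilot study") and says the team will try to recruit more.

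Apart from preliminary descriptive analyses, the Data Analysis section names no between-arm effect estimate, no confidence interval, and no way of reading a non-significant outcome.

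**The concern.** There are two gaps, and one change to the text closes both.

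First, the aim is set up as a question of significance in a study whose authors call its power low. The outcome of a test at this size says little about how large or small the effect could be. A non-significant result could come from no effect or from too few subjects, and the plan gives the reader nothing to tell these apart.

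Second, the sentence that says how impact will be recognised points to Time. A Time effect is a change from baseline to week 4 averaged over the arms. It can appear when both arms change equally, for instance after the educational session that every subject receives. The hypothesis concerns a difference between arms, and in this model that difference is carried by Group x Time. That is also the term the sample-size section says it powers.

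What is at stake is how informative and correctly targeted the pilot's reported result is for blood pressure, sodium intake and knowledge.

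**Working it through.** **Inputs from the documents (sample-size section):** f = 0.39, labelled a within-subject (Time) effect; 2 groups; 2 measurements; r = 0.5; alpha = 0.05; N = 28 analysed; 32 enrolled 1:1; stated power 70%. **Assumptions:** equal loss in the two arms, so 28 analysed is 14 per arm; two-sided testing; no outcome SD is given, so results are in SD units.

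**1. Can the stated 70% be reproduced?** Power comes from the noncentral F distribution with 1 and 26 df, with f² = 0.1521. Software conventions define the noncentrality differently:

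| Convention | Noncentrality at N = 28 | Power |
|---|---|---|
| Usual repeated-measures interaction, f² x N x 2/(1 - r) | 17.04 | 97.8% |
| f² x N x 2, no correlation term | 8.52 | 80.2% |
| Between-subject factor, f² x N x 2/(1 + r) | 5.68 | 63.1% |
| f² x N x (2 - 1) | 4.26 | 51.1% |
| f² x (N - 2) x (2 - 1) | 3.95 | 48.2% |

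None of these gives 70% at N = 28. The range is roughly 48% to 98%, and the documents do not say which definition of f was used. The attrition step does reproduce: 28/(1 - 0.11) = 31.5, rounded up to 32.

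**2. What 70% implies, taken at face value.** With 26 df the two-sided critical value is t = 2.056. Power of 70% needs a noncentrality of 2.581, that is, a true difference of 2.581 x sqrt(2/14) = 0.975 SD of the change.
- Chance of missing an effect of that size: 1 - 0.70 = 30%.
- Mean significant estimate divided by the true effect: 1.185, about 1.19.
- If the true effect is 75% or 50% of that size, power is 46% or 24%, so it is missed 54% or 76% of the time.

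**3. How far this depends on the 70%.** At 50% power the miss rate is 50% and the ratio is 1.38. At 97.8% power the miss rate is 2.2% and the ratio is 1.01. The figures in step 2 therefore hold only if 70% is right.

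**4. Precision, which does not depend on the power figure.** The 95% CI half-width for the between-arm difference in change, in SDs of the change, is t(0.975, 2n - 2) x sqrt(2/n).
- n = 14 per arm: 2.056 x 0.378 = 0.777.
- n = 16 per arm: 2.042 x 0.354 = 0.722.

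At r = 0.5 the SD of the change equals the SD of the outcome, because sqrt(2 x (1 - 0.5)) = 1, so the same numbers apply on that scale. The age covariate costs one df and moves the first value only from 0.777 to 0.778, before any gain from age explaining variance. If the true power were 70%, the half-width would be 2.056/2.581 = about 80% of the true effect.

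**The case against.** The strongest reply is that this is an openly exploratory aim in a pilot. Acceptability is the key Aim 2 outcome, the low power is disclosed, and the word *significantly* appears in a hypothesis, not in a decision rule. That is largely fair, and it limits what can be claimed.

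- A reader might infer that a real effect is likely to be reported as absent. For one outcome of the planned size at 70% power, detection is the more likely result; the miss rate is 30%. A miss becomes more likely than not only if the true effect is about three quarters of the planned size or less, or if one counts missing at least one of several outcomes (1 - 0.7³ = 66% for three, assuming independence and 70% power for each).
- A reader might infer that non-significance will be reported as no impact. The documents say no such thing; they simply do not rule it out.
- A reader might infer that an inflated estimate will be used to size a later trial. The documents mention no such use.
- A reader might want a rule that calls an interval inconclusive when it contains both zero and the planned effect. The plan gives a single f, taken from a blood pressure study, and no planned effect for sodium or knowledge, so that rule could not be applied.

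The exaggeration figure also depends on a 70% that cannot be reproduced, and on the highest reading it almost vanishes. What the reply does not answer is that the result is still not defined as a between-arm quantity, and that disclosing low power does not change what will be reported.

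**Conclusion.** The point stands as one about the definition and reporting of the result. The Exploratory Aim is framed as a significance test, its impact is read from a term that does not compare the arms, and no between-arm estimate or interval is made the result.

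The firm measure of size is precision: a half-width of about 0.78 SD of the change with 14 per arm, or 0.72 with 16. This assumes equal loss across arms and an approximately normal difference in change. The 30% miss rate and the ratio of 1.19 hold only if the plan's 70% power is correct, which its inputs do not confirm. That uncertainty is itself a reason to prefer an interval, since it shows the precision achieved whatever the true power was.

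**What to change.** In the SAP's Data Analysis section (Exploratory Aim), replace the sentence that reads impact from a Time effect with a statement to this effect: for each outcome, the result is the between-arm difference in change from baseline to week 4, estimated by the Group x Time contrast of the planned age-adjusted model, with its 95% confidence interval, reported whatever the p-value; a non-significant result will not be read as evidence of no impact.

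The Time-effect sentence has to be removed, not merely supplemented. Otherwise the SAP would give two different readings of impact.

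In the sample-size section, state the software option and the definition of f behind the 70%, or avoid relying on that figure when the results are interpreted.

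The cost is wording. Sample size, visits and data are unchanged, and the planned model already yields the contrast and its interval. The small downside is that the pilot gives up a yes/no claim of significance.

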MOBILE Intervention in College Students with Elevated Blood Pressure

Version Date: 05/19/2021

Protocol and Procedures

Protocol and Procedures

Aim 1 Formative research design. We will recruit two student panels (4-5 students each) to further refine the **MOBILE** intervention and assist in developing measures used in the study. We will recruit one set of student panel at a time. This 4-month phase will enable the team to design an extensive list of SMS messages tailored to different levels of motivation. In a 4-week intervention, enough messages are needed to ensure no message will be sent more than twice. Given 3 levels of motivation (1-low, 2-moderate, and 3-high), each level requiring different prompting messages, at least 42 (28 days x 3 levels = 84/2 = 42) messages need to be created across the 3 levels. The team will draft an initial set of messages, drawing content from the American Heart Association high BP recommendations;⁶⁰ each message's behavioral suggestions will correspond to each of the 3 motivation levels. Students will be surveyed to rank the effectiveness of each message; they will be asked to assess how clear, compelling, engaging, and motivating each message is in itself and how effective each message might be in propelling them to action. The investigative team will identify strong and weak messages, characterizing what makes strong messages strong. The team will then build a revised list of messages, discarding the weakest, or use what we have learned to strengthen the weaker messages. We will repeat this process with the second group of students using the revised list of messages and use those results to build a stronger final set of messages to be used in the implementation phase of the study. This iterative approach will also refine the study's motivational scale and self-report survey. This phase will be held via zoom with no in-person contact.

Aim 2 and Exploratory Aim Research Design. The proposed pilot study will use a randomized two-arm intervention and control group design to test the preliminary impact of the **MOBILE** intervention. The PI will be involved in all aspects of study and will train a research assistant (RA) to provide the educational session, monitor subjects, and address technology challenges.

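### The SAP names a 2x2x2 mixed ANCOVA when only two two-level factors are identified, and reads impact from Time instead of Group x Time

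*SAP*

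**What the plan says.** The SAP's Data Analysis section, under the Exploratory Aim, states the hypothesis as a comparison of arms: "The intervention group will have a significantly greater reduction in BP and sodium intake", with a greater rise in hypertension knowledge, relative to control. It then gives the model: "A 2x2x2 mixed design ANCOVA will be performed for each of the above primary and secondary outcomes". The same sentence goes on to name its terms: "with Study Group (Intervention vs. Control) as the between-subject factors, years of age as the covariate". The sentence after it gives the reading rule: "A Time effect on an outcome variable would indicate the impact of the" intervention. Group x Time is not mentioned in this section.

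The SAP's Sample size section, repeated in the Protocol under Aim 2 Sample size, describes a "mixed design ANCOVA with 2 groups, 2 measurements per subject" and a power target for the "significance test of the within-between interaction effect". The Protocol's Aim 2 and Exploratory Aim Research Design paragraph describes a "randomized two-arm intervention and control group design". Measurements are at baseline and four weeks later.

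**The concern.** There are two linked faults in consecutive sentences.

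- **The model label.** A 2x2x2 design has three two-level factors, and the documents supply two. The SAP uses the plural for between-subject factors but names one. Either a factor was left out or the label is a slip, and the text does not settle which. The model cannot be fitted as labelled until the third factor is named or removed.
- **The reading rule.** The randomised comparison is whether change differs between arms. A Time main effect asks whether the average change over both arms differs from zero. It can be significant when the arms changed identically, so the stated rule could credit the intervention with a change the controls also showed. Correcting the label alone would leave this rule in place.

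Shared change is plausible here. All subjects receive the educational session. Subjects whose second baseline blood pressure reading is below 120/80 mm Hg are dropped (Protocol, Baseline data collection), which favours a fall at follow-up in either arm.

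**Working it through.** **Step 1: count the factors.** 2x2x2 gives 8 cells.

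| Candidate | Role in the documents | Two-level factor? |
|---|---|---|
| Study Group | Intervention or control (SAP, Data Analysis) | Yes, between subjects |
| Time | Baseline and four weeks | Yes, within subjects |
| Age in years | Covariate | No |
| Two baseline BP readings | "will be taken twice, five minutes apart to be averaged" (Protocol, Baseline data collection) | No |
| Systolic/diastolic | Could apply to BP only; the same model is set for sodium intake and knowledge | No |

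Two factors remain, so 2 x 2 = 4 cells. That agrees with the 2 groups by 2 measurements in the Sample size section.

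**Step 2: what an omitted between-subject factor would cost.** Assume an even split.

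- Subjects per between-subject cell: 28/4 = 7 instead of 28/2 = 14; at N = 32, 32/4 = 8 instead of 32/2 = 16.
- Error df for Group x Time, from the change-score model: intercept, group and age give 28 − 3 = 25 (32 − 3 = 29). Adding the factor and its interaction with group gives 28 − 5 = 23 (32 − 5 = 27).

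The loss of df is small. The problem is that the model is undefined, not that it would be inefficient.

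**Step 3: how the Time test behaves when there is no intervention effect.** Let both arms change by the same amount d, in SD units of the outcome.

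- From the SAP: N = 28 evaluable or 32 recruited, r = 0.5, alpha = 0.05.
- Assumed: a two-sided test, age centred, and the values of d. The documents give no expected change in the control arm.
- SD of change = √(2(1 − r)) = √(2 × 0.5) = 1.
- Noncentrality = d√N / (SD of change), referred to a noncentral t with N − 3 df.
- Example: N = 28, d = 0.5 gives 0.5 × √28 / 1 = 2.646 on 25 df, a 72.0% chance of significance.

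| d (both arms) | Noncentrality, N = 28 | Time significant, N = 28 | Time significant, N = 32 |
|---|---|---|---|
| 0.25 | 1.323 | 25% | 28% |
| 0.50 | 2.646 | 72% | 78% |
| 0.75 | 3.969 | 97% | 98% |

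The correlation matters. At N = 28 and d = 0.5, r = 0.3 gives an SD of change of √1.4 = 1.183 and 58%; r = 0.7 gives √0.6 = 0.775 and 91%.

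Simulation of 20,000 trials per setting (N = 28, r = 0.5) gave 24.8%, 71.7% and 96.8% for Time, and 4.7%, 5.0% and 5.0% for Group x Time.

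The Sample size section is used here only for the design, N and r. Whether 70% power follows from its inputs is a separate question, and nothing above depends on it.

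**The case against.** The strongest reply is that the intent can be recovered. The hypothesis compares the arms, and the sample size text in both documents names two groups, two measurements and the within-between interaction. An analyst could fit the 2 x 2 model from that, and the Time sentence may be loose wording for change over time by group. This lowers the weight of the point. It does not remove it, because the analysis text never names Group x Time and states a different rule.

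Four further points are fair:

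- **Education and baseline timing.** The Protocol's Baseline data collection paragraph puts baseline before the educational session, but the Aim 2 Control Group paragraph puts the control arm's measurements after it. On the second reading, an immediate knowledge gain would not show as change in controls, so equal change is not a safe scenario for knowledge. Group x Time would not be clean either. If only the intervention arm's change contained an assumed education gain of 0.25, 0.5 or 0.75 SD, Group x Time would be significant in about 10%, 25% and 48% of trials (N = 28, r = 0.5, 25 df). The timing needs reconciling in its own right, but it does not turn Time into a comparison of arms.
- **Selection.** The 120/80 rule bears on blood pressure only, not on sodium intake or knowledge.
- **Centring.** The SAP does not say whether age is centred. If it is not, the Time term estimates change at age zero, and the 72% falls to about 13%, 8% or 6% for an assumed age mean/SD ratio of 3, 5 or 7. The percentages are therefore conditional. An uncentred Time term is no better a measure of impact.
- **Direction.** A significant Group x Time effect could favour control. The direction has to be taken from the hypothesis, which states it.

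**Conclusion.** The concern holds on both counts. The model label implies three factors where the documents identify two, and the reading rule conflicts with the SAP's own hypothesis and with the test named in its sample size section. The factor count and the conflict rest on the text alone.

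The 25%, 72% and 97% figures illustrate why the Time sentence must change. They assume an equal change of 0.25, 0.5 or 0.75 SD in both arms, r = 0.5, N = 28, a two-sided 5% test and centred age. They do not predict this trial's error rate. No consequence for power or multiplicity is claimed.

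The sponsor should make the correction. The consequence is low to moderate: it affects the Exploratory Aim of a pilot whose key Aim 2 outcome is acceptability.

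**What to change.** Amend two sentences in the SAP's Data Analysis section before analysis.

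1. **Model.** Confirm whether a third factor was intended. If not, specify a 2 (Study Group, between subjects) x 2 (Time: baseline and 4 weeks, within subjects) mixed ANCOVA with age as covariate, fitted separately for each outcome, with Group x Time as the tested term. If one was intended, name it, its levels and whether it is between or within subjects, and label it exploratory.
2. **Reading rule.** In either case replace the Time sentence. Suggested wording: A Group x Time effect on an outcome variable would indicate that change from baseline to 4 weeks differs between the arms; its direction is judged against the stated hypothesis.

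Stating that age is centred would make any reported Time term interpretable. The cost is SAP wording only, with no change to recruitment, sample size or data collection.
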